9.0 Safety Analyses

9.1 General Considerations

[figure not shown]
Safety data will be summarized separately by study Part for the Screening Confinement Set, Safety Analysis Set, and the Open Label Safety Analysis Set. For the Safety Analysis Set, safety summaries will be presented by regimen and overall. Subjects are assigned to a regimen based on the treatment actually received on the first day of dosing of the corresponding treatment period, regardless of the treatment randomized. For Part 1, safety analyses will be conducted using SC-P1, SA-P1 and OLSA-P1. For Part 2, safety analyses will be conducted using SA-P2 and OLSA-P2.

9.2 Adverse Events

Adverse events (AEs) will be summarized and presented using primary MedDRA SOCs and PTs according to the version of the MedDRA coding dictionary used for the study at the time of database lock. The actual version of the MedDRA coding dictionary used will be noted in the AE tables and in the clinical study report. Specific adverse events will be counted once for each subject for calculating percentages, unless stated otherwise. In addition, if the same adverse event occurs multiple times within a subject, the highest severity and level of relationship to investigational product will be reported.

9.2.1 AEs During the Screening Confinement Period

AEs and SAEs that have a start date either on or after the first day of the Screening Confinement Period, and up to the end day of the Screening Confinement Period will be summarized by SOC and PT for the Screening Confinement Set for Part 1 using SC-P1. Listing of SAEs during the Screening Confinement Period will also be provided for the Screening Confinement Set.

[figure not shown]

9.2.2 AEs During the Open Label Period(s)

AEs and SAEs that have a start date during an Open Label Period will be summarized by SOC and PT for the Open Label Safety Analysis Set for study Part 1 and Part 2 using OLSA-P1 and OLSA-P2, respectively. These AEs and SAEs include the following:

- For Part 2 and for Part 1 subjects enrolled under protocol amendment 6 or later:
 AEs and SAEs that have a start date either on or after the first dose date of OL
 Creon in Screening Period, and before the first dose of the study drug in DB
 Treatment Period 1 (if the subject entered the DB treatment period), or on or
 after the first dose date of OL Creon in the Screening Period (if the subjects
 never entered the DB treatment period)
- For Part 1 subjects enrolled under protocol amendment 5 or earlier: AEs and SAEs that have a start date either on or after the first dose date of the Maintenance Period, and before the first dose of the study drug in DB Treatment Period 1 (if the subject entered the DB treatment period), or on or after the first dose date of the Maintenance Period (if the subject never entered the DB treatment period)
- For Part 1 and Part 2: AEs and SAEs that have a start date either on or after the first dose date of the Open Label Period after DB Treatment Period 1, and before the first dose of the study drug in DB Treatment Period 2 (if the subject entered DB Treatment Period 2), or on or after first dose date of the Open Label Period after DB Treatment Period 1 (if the subject never entered the DB treatment period)
- For Part 2 and for Part 1 subjects enrolled after protocol amendment 6: AEs and SAEs that have a start date either on or after the first dose date of OL Creon in the Follow Up Period after DB Treatment Period 2

Listing of SAEs during the Open Label Period(s) will also be provided for the Open Label Safety Analysis Set.

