5.5.1 Treatments Administered

On completion of the screening visit the subject will be given a 30 day supply of open label Creon[®] at their usual pre-study daily dose (lipase units) of PERT to be taken until the subject comes back for Treatment Period 1 (if considered eligible). In exceptional circumstances, such as impact by COVID-19-related activities, this period may be extended by an additional 30 days upon specific consultation with the sponsor. Once results have been received and if it is deemed that a subject is not eligible, they will not receive any more open label Creon[®] and will be considered a screen failure.

For Part 1 of the study, study drug, consisting of Pancrelipase delayed release capsules MP 24,000 USP Units (Lipase) or Creon[®] (Pancrelipase) delayed release capsules

24,000 USP Units (Lipase) blinded capsules (same size, color and appearance), will be administered during DB Treatment Period 1 (Visit 2 to Visit 3) and DB Treatment Period 2 (Visit 4 to Visit 5) by the clinical site personnel at the time of each meal/snack as follows, depending on the treatment sequence arm the subject will be randomized to, as shown below:

Sequence Arm	Treatment Period 1	Treatment Period 2
А	Pancrelipase DR capsules MP	Creon [®] (Pancrelipase) DR capsules
В	Creon [®] (Pancrelipase) DR capsules	Pancrelipase DR capsules MP

DR = Delayed release; MP = Modernized Process uniform coated pellets, large scale

For Part 2 of the study, study drug, consisting of Pancrelipase DR capsules AAPIS, 24,000 USP Units (Lipase) or Creon[®] (Pancrelipase) delayed release capsules 24,000 USP Units (Lipase) blinded capsules (same size, color and appearance), will be administered during DB Treatment Period 1 (Visit 2 to Visit 3) and DB Treatment Period 2 (Visit 4 to Visit 5) by the clinical site personnel at the time of each meal/snack as follows, depending on the treatment sequence arm the subject will be randomized to, as shown below:

Sequence Arm	Treatment Period 1	Treatment Period 2
С	Pancrelipase DR capsules AAPIS	Creon [®] (Pancrelipase) DR capsules
D	Creon [®] (Pancrelipase) DR capsules	Pancrelipase DR capsules AAPIS

AAPIS = Delayed-release capsules of pancrelipase manufactured at an Alternate Active Pharmaceutical Ingredient Site; DR = Delayed release

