8.1.3 Safety Analysis

Safety analyses will be carried out using the Safety Analysis Set. Treatment-emergent AEs and SAEs, will be summarized and reported. Treatment-emergent AEs for DB Treatment Period 1 are defined as reported AEs that have a start date either on or after the first dose of the study drug during DB Treatment Period 1 and up to the end of DB Treatment Period 1. For DB Treatment Period 2, treatment emergent AEs are defined as reported AEs that have a start date either on or after the first dose of study drug during DB Treatment Period 2 and up to the end of DB Treatment Period 2. Adverse Events that occur during the administration of OL Creon[®] will be summarized separately for events that happen during the screening period and after randomization. The number and percent of subjects experiencing AEs will be tabulated by system organ class (SOC) and Medical Dictionary for Drug Regulatory Activities (MedDRA®) preferred term. In addition, summary of AEs by severity and relationship to study drug will be presented. Serious AEs, or AEs that lead to premature study discontinuation will be listed and described in detail. All these summaries will be done by treatment group. Mean change in vital signs and laboratory variables at each visit will be summarized. The last evaluation prior to the first dose of DB study drug in the corresponding treatment period will be used as baseline for the analysis in that treatment period. A frequency table will be presented for Potentially Clinically Important (PCI) vital sign findings. Shift tables for laboratory variables will be presented according to the reference ranges (low, normal or high).

Due to the small number of subjects per treatment group, only summary statistics will be applied to all the safety parameters.

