2.4 Sample Size Determination

The sample size determination consists of a power calculation for the total number of evaluable subjects needed and assumptions for percentage of drop-outs for the total number of subjects enrolled. A non-inferiority margin of 12% is chosen for the study. This non-inferiority margin for comparing Pancrelipase DR MP to Creon® (Part 1) or comparing Pancrelipase DR AAPIS to Creon® (Part 2) was derived based on Creon's effect in a more comparable subject population in the historical study with a similar study design as follows:

Based on historical data from 4 placebo-controlled studies (Studies S223.3.101¹, S223.3.102², S245.3.126³, S245.3.127⁴), the effect in CFA is 36.8% (95% confidence interval: 32.6% – 41.0%) comparing Pancrelipase DR Capsules 24,000 with placebo.

Specifically, in the historical placebo-controlled Creon® Study S245.3.126³, which had a similar study design as Study M16-111 (as a two-period, two-sequence cross-over study conducted in an adult population at the same dose strength as M16-111), the effect of Creon® compared to placebo in CFA was estimated as 39.02% (95% CI: 32.3% – 45.8%) based on 31 enrolled CF subjects with confirmed EPI based on the eligibility criteria of a historical CFA < 70%, or current or historical Fecal Elastase-1 (FE-1) < 50 μ g/g. However, it is expected that the current Study M16-111 will enroll subjects with more severe EPI than the subjects in Study S245.3.126, as the enrollment criteria for EPI in the current study is more stringent: subjects need to have a baseline FE-1 less than 15 μ g/g to be enrolled. At the time of the protocol amendment 6, all subjects enrolled (N=10) in Study M16-111 had a screening FE-1 of less than 15 μ g/g and a screening CFA below 50%.

A subgroup analysis in Study S245.3.126 was performed to estimate the Creon effect in subjects with a more severe EPI, defined as having a CFA of 50% or less during the placebo treatment period (since the screening FE-1 value was not collected in Study S245.3.126). The Creon effect compared to placebo in CFA was estimated as 52.25% (95% CI: 47.0% - 57.5%) in this subject population. Based on the lower bound of the 95% CI for the estimate of Creon effect, a non-inferiority margin of 12% would preserve over 70% of that effect ((47-12)/47=74%).

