For each study Part, it is assumed that the expected difference in means of CFA between Creon® and Pancrelipase DR MP (Part 1) or between Creon® and Pancrelipase DR AAPIS (Part 2) is 0. For Part 1, with 22 subjects who complete the two crossover treatment periods and have valid CFA as the primary endpoint, the power of the study to claim non-inferiority by comparing the 99% confidence interval (CI; i.e., based on one-sided type I error of 0.005) with a margin of 12% is approximately 96%, assuming a standard deviation (SD) of 12% for the within-subject treatment difference.

For Part 2, with 18 subjects completing the 2 crossover treatment periods and having valid CFA in both periods, the power to claim non-inferiority is approximately 98% based on one-sided type I error of 0.005 (i.e., based on two-sided 99% CI for non-inferiority

assessment with a margin of 12%), assuming a standard deviation (SD) of 10% for the within-subject treatment difference (see Section 2.4.1 for justification of 10% SD based on BSSR).

Table 1. Study Power for Non-Inferiority in Primary Endpoint of CFA

SD of Treatment Difference	Power (N=22)	Power (N=18)
8%	99%	99%
10%	99%	98%
12%	96%	89%
14%	87%	75%

Note: Power for non-inferiority in primary endpoint by evaluable sample size, if true CFA difference is 0.

It is expected that a screening failure rate of about 30% will be observed and that approximately 10-15% of the subjects will drop out during the treatment periods. Based on these assumptions, approximately 36 subjects will be screened and approximately 26 subjects will be randomized in Part 1 to expect 22 subjects to complete the crossover treatment periods with evaluable CFA in both treatment periods, and approximately 30 subjects will be screened and approximately 20 subjects will be randomized in Part 2 to expect 18 subjects to complete the crossover treatment periods with evaluable CFA in both treatment periods.

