4.0 Analysis Populations

The following population sets will be defined and used for the analyses for each study Part.

[figure not shown]
The Screening Confinement Set consists of all subjects who started screening confinement. The screening confinement period was removed from the study design in protocol amendment 6. Therefore, the Screening Confinement Set (denoted SC-P1) is only defined for Part 1 and includes subjects screened under protocol Amendment 5 or earlier.

The Intent-to-Treat (ITT) Population includes all randomized subjects in each study Part (denoted as ITT-P1 and ITT-P2 for Part 1 and Part 2, respectively). Subjects will be included in the analysis according to the treatment sequence to which they are randomized.

The Evaluable Set (ES) consists of all randomized subjects in each study Part who complete both double-blind (DB) treatment periods and have 100% of stool samples collected and analyzed by the laboratory and valid total fat intake value for both DB treatment periods. The ES for Part 1 and Part 2 will be denoted as ES-P1 and ES-P2, respectively. Subjects will be included in the analysis according to the study drug that they actually received.

The Safety Analysis Set consists of all randomized subjects who received at least 1 dose of study drug in the DB treatment periods in each study Part (denoted as SA-P1 and SA-P2 for Part 1 and Part 2, respectively). Subjects will be included in the analysis according to the regimen that they actually received.

The Open Label Safety Analysis Set in each study Part consists of all subjects who received at least 1 dose of open label Creon during any study period (denoted as OLSA-P1 and OLSA-P2 for Part 1 and Part 2, respectively). For Part 1, subjects who received open label Creon during the maintenance period (only applicable for subjects enrolled prior to protocol amendment 6) will also be included in OLSA-P1.

For Part 1, the population sets include: the Screening Confinement Set (SC-P1), Intent-to-Treat Population (ITT-P1), Evaluable Set (ES-P1), Safety Analysis Set (SA-P1) and Open Label Safety Analysis Set (OLSA-P1). For Part 2, the population sets include: the Intent-to-Treat Population (ITT-P2), Evaluable Set (ES-P2), Safety Analysis Set (SA-P2) and Open Label Safety Analysis Set (OLSA-P2).

[figure not shown]

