6.0 Study Drug Duration and Compliance

[figure not shown]
For the Safety Analysis Set, duration of double-blind treatment will be summarized per treatment period for each regimen using SA-P1 and SA-P2 for study Part 1 and Part 2, respectively. Duration of treatment is defined for each subject as last dose date of the corresponding DB treatment minus first dose date of the corresponding DB treatment + 1. Duration of treatment will be summarized using the number of subjects treated, mean, standard deviation, median, minimum and maximum.

Descriptive statistics will also be provided for average lipase units/fat (g) intake in Days 3 - 5 and average lipase units/weight (kg) in Days 3 - 5 per regimen during the DB treatment periods for the Safety Analysis Set. In addition, the number and percentage of subjects will be summarized by categorized average lipase units/fat intake (g) in Days 3 - 5 for the following categories:

- < 2500

- 2500 3500
- 3500 4500
- 4500 5500
- > 5500

Treatment compliance in each DB treatment period will be summarized by regimen and overall for the Safety Analysis Set. Treatment compliance in each DB treatment period is defined as the number of capsules taken divided by the number of capsules that should have been taken in Days 3 - 5 of that treatment period.

The number and percentage of subjects who are at least 90% treatment compliant with study drug administration will be summarized for each DB treatment period. In addition, compliance rate will be summarized using the number of observations, mean, standard deviation, median, minimum and maximum for each DB treatment period.

[figure not shown]

In addition, duration of exposure to open-label (OL) Creon during the period prior to randomization (for subjects who are never randomized, this will be the screening period or maintenance period when OL Creon is administered), will be summarized for the Open Label Safety Analysis Set for study Part 1 and Part 2 using OLSA-1 and OLSA-2, respectively. For OLSA-1, this includes the Maintenance Period (for subjects screened before protocol amendment 6) and the Screening Period (for subjects screened after protocol amendment 6). Duration of treatment is defined for each subject as last dose date of OL Creon prior to Visit 2 minus first dose date of OL Creon + 1. Duration of treatment will be summarized using the number of subjects treated, mean, standard deviation, median, minimum and maximum.

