Duration of exposure to OL Creon between DB Treatment Period 1 (TP1) and DB Treatment Period 2 (TP2) and after TP2 will be summarized for the Safety Analysis Set for study Part 1 and Part 2 using SA-P1 or SA-P2, respectively. Duration of treatment is defined for each subject as last dose date of OL Creon prior to Visit 4 minus first dose date of OL Creon after Visit 3 + 1 plus last dose date of OL Creon after Visit 5 minus first dose date of OL Creon after Visit 5 + 1. In other words, the total duration for the interval between TP1 and TP2, and the period after TP2 will be summed to calculate the duration of open-label treatment following randomization. Duration of treatment will be summarized using the number of subjects treated, mean, standard deviation, median, minimum and maximum.

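### Does SAP 9.2.2 need changing because it does not restate the protocol's before/after-randomization split of open-label adverse events or settle the changeover date?

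*SAP*

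**What the plan says.** Protocol 8.1.3 (Safety Analysis) states that adverse events arising on open-label Creon "will be summarized separately for events that happen during the screening period and after randomization".

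SAP 9.2.2 gives one instruction: "AEs and SAEs that have a start date during an Open Label Period will be summarized by SOC and PT", by Part, on the Open Label Safety Analysis Set (OLSA). Four bullets then define the qualifying windows: screening, maintenance (Part 1 subjects enrolled under Amendment 5 or earlier), the interval between blinded periods, and follow-up. SAP 4.0 defines OLSA as the set that "consists of all subjects who received at least 1 dose of open label Creon during any study period".

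For exposure, SAP 6.0 does separate the two phases. Pre-randomization duration is summarized on OLSA, with the note that "for subjects who are never randomized, this will be the screening period or maintenance period when OL Creon is administered". Interval and follow-up durations are "summed to calculate the duration of open-label treatment following randomization", on the Safety Analysis Set.

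SAP 9.2.3.1 ends the treatment-emergent window of Period 1 at the earliest of three points: the first open-label dose date after Visit 3, the start of Period 2 dosing, or 30 days after the last blinded dose. Period 2 ends at the earlier of the first open-label dose date after Visit 5 or 30 days after the last blinded dose. The open-label windows in 9.2.2 include the first open-label dose date.

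**The concern.** Read alone, SAP 9.2.2 could be met by one table per Part that pools events before and after randomization. OLSA can include people who were never randomized: protocol 5.5.1 dispenses open-label Creon at screening and says that "if it is deemed that a subject is not eligible, they will not receive any more open label Creon". They cannot have post-randomization events, so they do not belong in the denominator for those events. The protocol's two summaries might then not appear.

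The second worry is the changeover date. If the blinded window includes the first open-label dose date, an event on that date is in both the treatment-emergent and the open-label tables. If it excludes the date, an event on a day when blinded drug may also have been taken is shown only as open-label. Two programmers could then report different double-blind counts.

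**Working it through.** **1. Can the protocol's split be made from the SAP's windows?**

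| SAP 9.2.2 window | Side of randomization |
|---|---|
| Screening, Part 2 and Part 1 under Amendment 6 or later | Before |
| Maintenance, Part 1 under Amendment 5 or earlier | Before |
| Interval after blinded Period 1 | After |
| Follow-up after blinded Period 2 | After |

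No window straddles randomization for a randomized subject. Sorting events by bullet gives the two summaries in protocol 8.1.3, and nothing in 9.2.2 forbids it. SAP 6.0 shows the matching denominators: OLSA before, Safety Analysis Set after.

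**2. Which table takes an event near the changeover?** Illustrative study days: first blinded dose day 1, last blinded dose of Period 1 day 7, first dose of Period 2 day 30. TE = treatment-emergent, OL = open-label.

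| First open-label dose | End of blinded window read as | Day 6 | Day 7 | Day 8 | Day 9 |
|---|---|---|---|---|---|
| Day 7 | inclusive | TE | both | OL | OL |
| Day 7 | exclusive | TE | OL | OL | OL |
| Day 8 | inclusive | TE | TE | both | OL |
| Day 8 | exclusive | TE | TE | OL | OL |

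The pattern after Period 2 is the same (first open-label dose on day 36 or 37). The readings differ on one date per changeover, so on at most two dates per subject per Part.

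**3. Does the text favour a reading?** SAP 9.2.2 places the date in the open-label window outright. In 9.2.3.1 the same end rule also covers the start of Period 2 dosing, and the Period 2 window opens at that dose. An inclusive end would make the two regimens' windows meet at the same point; an exclusive end keeps them apart. SAP 9.2.1 words the end of the screening confinement window in a way that reads as inclusive, but it names an end day and concerns a period that Amendment 6 removed.

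**4. How far could a pooled denominator matter?** No document says how many never-randomized subjects took open-label Creon, so these figures are illustrations, not bounds. Planned screened minus randomized is 36 − 26 = 10 in Part 1 (10/36 = 28%) and 30 − 20 = 10 in Part 2 (10/30 = 33%). SAP 2.4 expects that "a screening failure rate of about 30% will be observed", which gives 0.30 × 36 = 10.8 and 0.30 × 30 = 9. If every screened subject took open-label drug and counted towards that Part, a post-randomization percentage on OLSA would be 26/36 = 0.72 (Part 1) or 20/30 = 0.67 (Part 2) of the percentage among randomized subjects. If none did, the ratio would be 1. The assumption is weak. Protocol 5.1 allocates subjects to a Part only at Visit 2, together with randomization, and subjects taking part in both Parts may skip most of the second screening.

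**The case for a change.** The best case for a change is that one pooled table would satisfy the SAP's wording while departing from the protocol's. SAP 9.2 counts each specific event once per subject, so separate incidences could not be recovered from that table. The authors split exposure explicitly in SAP 6.0, which makes the omission in 9.2.2 more noticeable. Shared dates are also plausible: blinded drug continues until the last stool is collected, discharge follows, and open-label drug is dispensed at that point. For direct entry into Period 2, Visit 4 is the day after Visit 3, with open-label Creon in between.

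Part of this stands. The SAP does not state the split for adverse events, and it does not say in words whether the blinded window includes its end date. But the harm requires an analyst to apply the SAP and ignore a plain sentence in the protocol that the SAP does not contradict. On direct entry, the Visit 3 date is the realistic shared date; Period 2 dosing starts at breakfast on Visit 4, so a first open-label dose that day is unlikely. Assigning the shared date to the blinded regimen instead would be another convention, and it would run against the start rule in 9.2.2. An event that appeared in both tables would not distort a total, because no planned summary adds them.

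**Conclusion.** No change follows. This is missing detail that an analyst working from both documents fills in the ordinary way: two open-label summaries, each with the denominator SAP 6.0 already uses for exposure, and changeover-date events in the open-label table as 9.2.2 places them.

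The reach is small. Only descriptive adverse-event tables are touched, serious events are also listed individually, and any table can be re-cut from recorded dates. The primary comparison of fat absorption and the secondary endpoints use no adverse-event data. At the target numbers of completers the changeover dates are at most 18 × 2 = 36 in Part 2. In Part 1 they are at most 22 + 16 = 38, where 16 = 26 randomized − 10 enrolled by Amendment 6, since the follow-up window in 9.2.2 covers only Part 1 subjects enrolled after it. These are dates, not events. The number of events on them, and the direction of any effect on a percentage, cannot be determined from the documents.

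The conclusion assumes that protocol 8.1.3 remains in force alongside the SAP, and that the end of the blinded window is read as exclusive. If it is read as inclusive, some events appear in two separate descriptive tables and no conclusion of the trial changes.

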Part 2 DB Treatment Periods 1 and 2	Periods during which subjects are taking study drug Creon [®] (pancrelipase) Delayed Release capsules 24,000 USP Units (lipase) or pancrelipase DR capsules manufactured with an Alternate Active Pharmaceutical Ingredient Site (AAPIS) 24,000 USP Units (lipase) every day at the time of meals/snacks.
	Part 2, DB Treatment Period 1 starts at Visit 2 and ends at Visit 3 and is separated by an interval of up to 28 days from DB Treatment Period 2, which starts at Visit 4 and ends at Visit 5.
Post-Treatment Follow-up Period for subjects participating in only one study Part (Part 1 or Part 2)	Interval between the last dose of study drug (Visit 5) and the safety follow-up telephone contact (Visit 6). During this period subjects will receive open label Creon [®] (Pancrelipase) 24,000 USP units (lipase).

Post-Treatment Follow-up Periods for subjects participating in both study Parts (Part 1 and Part 2) Interval between the last dose of study drug (Visit 5) of the study Part the subject was originally assigned to and Visit 6 of that Part, or Visit 1 of the next study Part, whichever comes first. This period is variable in duration, and can last up to 30 days. During this period, subjects will receive open label Creon[®] (Pancrelipase) 24,000 USP units (lipase). If visit 1 of the next Part does not occur within 30 days of the last dose of study drug (Visit 5) of the previous part, the subject will not receive any additional open label Creon[®] (Pancrelipase) 24,000 USP units (lipase) 24,000 USP units (lipase) 24,000 USP units (lipase) and the subject will need to be re-consented and rescreened for the next study part.

Once the subject has completed Visit 5 of the next study Part, the follow up period of that next Part is the interval between the last dose of study drug (Visit 5) and the safety follow-up telephone contact (Visit 6) and is 30 days. During this period subjects will receive open label Creon[®] (Pancrelipase) 24,000 USP units (lipase).

abbvie	Pancrelipase M16-111 Protocol Amendment 7
	EudraCT 2017-000578-12

2.0	Table of Contents	
1.0	Title Page	1
1.1	Protocol Amendment: Summary of Changes	2
1.2	Synopsis	4
1.3	List of Abbreviations and Definition of Terms	8
2.0	Table of Contents	12
3.0	Introduction	1 6
3.1	Differences Statement	17
3.2	Benefits and Risks	17
4.0	Study Objective	18
5.0	Investigational Plan	18
5.1	Overall Study Design and Plan: Description	18
5.2	Selection of Study Population	27

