9.2.3.1 Treatment-Emergent Adverse Events

Treatment-emergent AEs for the regimen administered in DB Treatment Period 1 are defined as reported AEs that have a start date either on or after the first dose of the study drug during DB Treatment Period 1, and up to the end of DB Treatment Period 1, defined as the earliest of: the first dose date of OL Creon after Visit 3, the start of the first dose of DB Treatment Period 2, or 30 days after the last dose of study drug during DB Treatment Period 1. For the regimen administered in DB Treatment Period 2, treatment emergent AEs are defined as reported AEs that have a start date either on or after the first dose of study drug during DB Treatment Period 2, and up to the end of DB Treatment Period 2, defined as the earlier of the first dose date of OL Creon after Visit 5 or 30 days after the last dose of study drug during DB Treatment Period 2.

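### SAP 9.2.2 sets a condition no subject can meet for open-label adverse events after Period 1, so its listed windows omit subjects who never start Period 2

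*SAP*

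**What the plan says.** SAP 9.2.2 opens with a general rule: "AEs and SAEs that have a start date during an Open Label Period will be summarized". It then introduces four bullets with "These AEs and SAEs include the following".

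- The first two bullets cover open-label Creon before randomised treatment.
- The third covers open-label Creon after Period 1. Its first branch ends "before the first dose of the study drug in DB Treatment Period 2 (if the subject entered DB Treatment Period 2"). Its second branch starts at the first open-label dose "after DB Treatment Period 1 (if the subject never entered the DB treatment period").
- The fourth covers events "on or after the first dose date of OL Creon in the Follow Up Period after DB Treatment Period 2". It gives a start and no end.

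SAP 9.2.3.1 closes the Period 1 treatment-emergent window at the earliest of three dates: "the first dose date of OL Creon after Visit 3", the first Period 2 dose, or 30 days after the last Period 1 dose.

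SAP 6.0 measures open-label exposure after Period 2 as "last dose date of OL Creon after Visit 5 minus first dose date of OL Creon after Visit 5 + 1", also without a stated end.

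The documents do define that end elsewhere. For subjects in both Parts, the note to SAP Figure 1 (SAP 2.2) ends the first Part's follow-up at Visit 6 or on the day before the next Part's Visit 1, whichever is earlier. Protocol 1.3 says "Visit 6 of that Part, or Visit 1 of the next study Part, whichever comes first".

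**The concern.** The bullets are the date rules a programmer would code. In the third bullet, the second branch should catch everyone the first branch leaves out, namely subjects who took open-label Creon after Period 1 and did not go on to Period 2. Instead it asks for subjects who were never in double-blind treatment at all. That group is empty, because the bullet begins after Period 1.

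The protocol creates the group that is missed. Under Protocol 5.4.1, a subject without complete stool collection in a confinement period may not begin the next one in that Part. Under Protocol 5.3.1.1, a positive pregnancy test at Visit 4 ends participation. Protocol 5.5.1 supplies open-label Creon at the end of Period 1. What is at stake is whether adverse events in subjects who stop between periods appear in the open-label tables, or depend on a programmer guessing the intent.

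**Working it through.** **Step 1. Run the written windows on hypothetical subjects.** Day 0 is the first open-label dose at screening. Period 1 runs from day 30 to day 36.

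- *Subject A* starts open-label Creon on day 37 and never starts Period 2. Take events on days 40 and 60 (3 and 23 days after the open-label start).
  - Third bullet, first branch: not met, because there is no Period 2.
  - Third bullet, second branch: not met, because Period 1 was entered.
  - Fourth bullet: not met, because there is no follow-up after Period 2.
  - Period 1 treatment-emergent window: closed on day 37.
  - Result: no listed window. With the condition changed to Period 2, both events fall in the third bullet.
- *Subject B* never starts Period 2 and takes no open-label Creon. Events on days 40 and 60 (4 and 24 days after the last dose) are Period 1 treatment-emergent events, because the window runs to day 36 + 30 = 66. The gap does not affect this subject.
- *Subject C* completes both periods, starts follow-up Creon on day 67 and joins the other Part. First-Part follow-up ends on day 86, and the next Part's Period 1 runs from day 90 to day 96. An event on day 92 satisfies the fourth bullet only if that bullet is read alone. Once the lead sentence or the Figure 1 end of follow-up is applied, it does not.

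For subject A it is assumed that Visit 3 took place. If a subject stops during Period 1 and has only an early-termination visit, the Period 1 cut-off, which is tied to Visit 3, must be read as applying to that visit.

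**Step 2. Check that follow-up is meant to be bounded.** Protocol 5.1 gives maximum durations of about 109 days (one Part) and 183 days (both Parts).

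- One Part: screening 35 + Period 1 8 + interval 28 + Period 2 8 + follow-up 30 = 109 days.
- Second Part: 8 + 28 + 8 + 30 = 74 days, and 109 + 74 = 183 days.

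Both figures are reproduced with a 30-day follow-up in each Part. The fourth bullet omits an end that the plan already has.

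**Step 3. Size.** From Protocol 8.2.2:

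- Part 1: 26 randomised − 22 completing = 4 (4/26 = 15%).
- Part 2: 20 − 18 = 2 (2/20 = 10%).
- Together: 6 of 26 + 20 = 46 randomisations (13%). The stated 10–15% drop-out applied to 46 gives 4.6 to 6.9, which agrees.

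Six is a ceiling on the planned number affected. It includes subjects who stop during Period 2, and only those who stop before Period 2 and take open-label Creon meet the gap.

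**The case against.** The strongest reply is that the lead sentence of SAP 9.2.2 is the operative rule and the bullets only illustrate it. On that view an open-label event after Period 1 is included whether or not Period 2 starts. Protocol 8.1.3 likewise calls for events on open-label Creon after randomisation to be summarised, and the open-label safety set in SAP 4.0 takes in anyone with a single open-label dose. The slip also corrects itself: the first branch names Period 2, so its complement must too, and the same phrase is correct in the first two bullets.

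This stands as evidence of intent. A reader might infer that these events meet no rule at all, and the documents do not support that. It does not remove the conflict between the lead sentence and a bullet that, when coded, returns nobody.

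Two further inferences are also unsupported.

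- *Blinded events of the next Part are counted under the previous Part's open-label Creon.* Such events do not start in an open-label period, SAP 1.0 keeps analyses within each Part, and the Figure 1 note ends follow-up before the next Visit 1. What remains is narrower: open-label interval events of the next Part do satisfy the lead sentence and the fourth bullet's start date. Only the within-Part rule and a figure note keep them out, so an explicit end date is worth adding.
- *Part 1 subjects enrolled under Amendment 6 are excluded because the first bullet speaks of that amendment or later and the fourth of after it.* SAP 6.0 uses after Amendment 6 as the counterpart of before it, with no third group, so no error is shown.

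On SAP 6.0, the text following the formula says that it sums the interval between periods and the time after Period 2. The intent is clear there too, and only the end date is unstated.

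**Conclusion.** The point holds as a wording error in the third bullet of SAP 9.2.2 that conflicts with the section's lead sentence. Read as a date rule, it omits open-label events in subjects who have been through Period 1, take open-label Creon and never start Period 2. The missing end dates in the fourth bullet and in SAP 6.0 are a lesser matter of consistency.

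The effect is confined to descriptive open-label safety tables, for at most some of about 6 planned non-completers. This rests on the planned drop-out; the documents do not say how many subjects stop between periods. The regimen comparison uses treatment-emergent events in the Safety Analysis Set, and the primary analysis uses the Evaluable Set, so neither is affected. Protocol Figure 2, on adverse event collection by Part, is not reproduced in the text available and could not be checked.

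**What to change.** In the third bullet of SAP 9.2.2, make the second condition refer to subjects who never entered *DB Treatment Period 2*.

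As a consistency edit, add the end date already in the SAP Figure 1 note (Visit 6 of that Part or the day before the next Part's Visit 1, whichever is earlier) to the fourth bullet and to the post-Visit 5 exposure formula in SAP 6.0. The corrected branch of the third bullet has no end date either and should take the same one, since Protocol 5.4.1 allows a subject discontinued from one Part to be offered the other.

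The cost is a few wording changes before the safety tables are programmed. No design, data collection, sample size or efficacy analysis changes.
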